The FRS was developed by Wilson et al in 1998 and has become standard of care for estimating risk of a cardiovascular event over the next 10 years. The estimation takes gender, age, smoking status, systolic blood pressure, total cholesterol and HDL into account when predicting risk (4). Scores are converted into percentage of risk over the next 10 years using a table created by Wilson et al. Individuals with scores of 0-10% are considered low risk. A score of 11-15% indicates low-moderate risk, while a score of 16-20% indicates mod-high risk. Those with scores of >20% are considered high risk, while those with known coronary artery disease or acute coronary syndrome are considered very high risk (2). While the FRS at times is a basis for treatment decisions, this system of calculating risk is not individualized, and does not take into account other contributing factors such as family history, weight, etc.

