CAC scores are reported as a numerical value and a percentage for age that is then regarded in terms of risk categories. A score of zero with no cardiovascular risk factors indicates no evidence of CAD and thus a very low risk of cardiovascular event in the next ten years. If the individual has cardiovascular risk factors with a CAC score of 0, they are considered moderately low risk. A score of 1-100 and a percentage for age percentile less than 75% indicates mild to moderate evidence of CAD and therefore indicates moderately high risk. A score of 101-399 or a percentage for age greater than 75% indicates moderate to high evidence of CAD and therefore is considered high risk with possible current partial blockage of coronary arteries. A score of >400 or any CAC score >100 with a >90% percentage for age indicates extensive evidence of CAD and thus high risk of cardiovascular event in the next ten years and could indicate further testing is needed to address potential majority blockage (9, 10).

A consensus report issued by the American College of Cardiology and the American Diabetes Association emphasizes the concept of a global cardio metabolic risk. Factors that increase the risk of cardiovascular disease include dyslipoproteinemia, hypertension, diabetes and the prediabetic states such as insulin resistance or hyperglycemia, and central obesity. Smoking and sedentary lifestyle exacerbate the risk. The epidemic rise in the prevalence of one or more of these risk factors has created a heterogeneous population at risk that is perhaps not well represented by the traditional Framingham study population, which commenced in 1948.

The American College of Cardiology (ACC) and the American Heart Association (AHA) recognize the incremental benefit of CAC screening and endorse its use in intermediate risk individuals with a FRS between 10-20%. The SHAPE (Screening for Heart Attack Prevention and Education) Task Force report goes further, publishing guidelines calling for the use of CAC scanning or CIMT as part of a nation-wide screening program to detect CAD in males 45 years and older, and females 55 years and older (10).

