It is tempting to conclude from this study that population health initiatives in the US, and more specifically the military, have led to a dramatic decline in rates of atherosclerosis in our younger population. It is also tempting to conclude that the current military lifestyle represents a model for healthy living and one that perhaps should be adopted by the US population as a whole. However, this conclusion is assuming that the warriors who died are both representative of the younger US population as a whole and the broader US military population, respectively. An alternative explanation for the findings by Webber et al. may be that the US service members accounting for the majority of deaths from combat and unintentional injuries are indeed healthier, but are not representative of the military community at large. Service members must undergo a thorough health and fitness screening process prior to each deployment. Members that do not pass are not deployable. Furthermore, within each service, there are additional screening measures for entry into occupations that are more likely to expose a service member to the risks of combat. The “healthy warrior” phenomenon, therefore likely exists only after multiple layers of screening, and is not likely present within the greater US military population.

Based on the prevalence of obesity and accompanying cardiovascular disease risk factors mentioned above, the military population is unlikely to be much healthier than the age-matched US population. In fact, it may be that the rates of atherosclerosis in US service members are higher than in their civilian counterparts. It is quite possible that the environment and lifestyle of the military may both select for and exacerbate cardiovascular risk. The Prospective Army Coronary Calcium Project, as reported by Taylor et al, showed that traditional cardiac risk prediction tools significantly underestimate subclinical atherosclerosis in a low risk unselected screening cohort of 650 active duty Army personnel between the ages of 39-45 years of age (18). The prevalence of coronary calcium was 20.6% for males and 4.3% for females. In a 3 year follow up of 2000 subjects from this study, coronary calcium was associated with an 11.8 fold increase in cardiovascular events in males. There were no events in women in this study, likely due to low numbers. The study also deemed calcium scoring cost effective at \$37,633 per quality-adjusted life year saved.

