Given that the true rates of atherosclerosis within the greater military population are unknown and that the cluster of cardio metabolic risk factors are present at a relatively young age and in greater numbers than the general population, we aim to study the prevalence of subclinical atherosclerosis in US enlisted service members with one or more cardio metabolic risk factor using coronary artery calcium scoring with cardiac computed tomography. While the military has not adopted the SHAPE Task Force guidelines, or any other screening protocol involving imaging based modalities, the value of using risk factors to select individuals who may stand to benefit from the greater predictive power of coronary artery calcium scoring may prove to be useful in this population. This approach could be key to understanding the prevalence of subclinical atherosclerosis, measuring the effect of population health initiatives on rates of atherosclerosis over time and ultimately improving our ability to meet the stated objective of DoD health promotion, which is to return the veteran back to society in relatively good health.

6.2. Hypotheses or Research Questions or Objectives:

Hypothesis: Enlisted military members with 10 or more years of service and at least one cardiovascular risk factor will demonstrate a higher risk of future cardiac events as assessed by coronary artery calcium scoring than the risk calculated by the Framingham Risk Score.

The primary aims of this study are as follows:

- 1) Determine prevalence of atherosclerosis in active duty enlisted military members with 10 or more years of military service and at least one cardiovascular risk factor using coronary artery calcium scoring.
- 2) Assess the rate of reclassification of subjects from one risk category using Framingham Risk Scores (FRS) to another risk category using the results of the Coronary Artery Calcium (CAC) score.
- 3) Compare FRS to the CAC percentage for age risk score for enlisted subjects with at least 10 years of military service and at least one additional cardiovascular risk factor to determine how well the results correlate with one another.

The secondary aims of this study are as follows:

- 1) Compare CAC scores between each group in the following categories to see if there is associations between these categories and formation of calcified plaques:

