- Subject will undergo one cardiac CT scan. Appointment for scan will take 10-20 minutes, the majority of which will be subject check in and positioning. Average radiation exposure for a CAC CT is 0.89 millisieverts (mSv). For context, the average population radiation exposure from background is approximately 3.11 mSv at sea level (4.5 mSv at high altitude), meaning

For Protocol Office use only:

Protocol title: Assessment of Coronary Artery Calcium in Active Duty
Enlisted Military Members with 10 or More Years of Service
FDG20130024H Protocol v15 w Amend 9

[figure not shown]
name redacted 6Feb20

DGMC Human Research Protocol

that the dose from this study is less than half of a person's baseline annual dose from sources such as cosmic radiation. Furthermore, a mammogram is approximately 0.73 mSv.

- **Incidental Findings:** As per usual radiology operating procedure, all cardiac CT scans will be reviewed in their entirety for any abnormalities. The report will be placed in CHCS/AHLTA and can be reviewed by the subject's primary care physician. The radiologist reading the films will also make follow-up recommendations for any concerning abnormal findings. The abnormalities will be brought to the attention of the provider who orders the cardiac CT. That provider will then inform the PI or AI of any abnormal findings. The PI/AI will then inform the subject of these findings as well as the follow-up recommendations of the radiologist. An encrypted e-mail will be sent to the subject's primary care physician if incidental findings are discovered.

Study Flow Chart (displayed on following page):

6.6. Data Collection/Analysis:

Sample Size/Power Analysis

- Based on an 8.5% expected prevalence of atherosclerosis in the active duty military population, the sample size requirement for a 95% confidence interval for a proportion of +/- 0.05 is 120 subjects. As the prevalence among active duty with >10 years of military service and at least one cardiovascular risk factor is likely higher, for this study the estimated prevalence is 10%. The sample size requirement for a 95% confidence interval for a proportion +/- 0.05 with a prevalence of 10% is 138 subjects. For this study, anticipated failure of completion/drop out is estimated to be approximately 10%, so 150 male volunteers will be recruited to achieve this confidence interval for prevalence of active duty atherosclerosis in enlisted members

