with 10 or more years of military service. Females do not tend to demonstrate coronary artery calcium in the same manner/degree as males. Therefore an additional pilot sample of 30 female volunteers will be used to assess the prevalence detected in the female active duty population.

Data Analysis

- Primary Aims:
 - Determine prevalence of atherosclerosis in active duty enlisted military members with 10 or more years of military service using coronary artery calcium scoring.
 - A 95% confidence interval will be calculated for the observed prevalence in the active duty population.
 - Assess the rate of reclassification of subjects from one risk category using Framingham Risk Scores (FRS) to another risk category using the results of the Coronary Artery Calcium (CAC) score.
 - For the purposes of this study, the SHAPE guidelines will be used to classify the CAC scores and percentage by age into the following categories:
 - Low Risk: CAC of 0 and no cardiovascular risk factors
 - Low-Moderate Risk: CAC of 0 with cardiovascular risk factors
 - Moderate-High Risk: CAC 1-100 *and* percentile for age <75%
 - High Risk: CAC 100-399 *or* percentile for age >75%
 - Very High Risk: CAC >100 *and* percentile for age >90% *or* CAC >400
 - For the purposes of this study, the FRS percentages will be classified into the following categories:
 - Low Risk: FRS 0-10%
 - Moderate Risk: FRS 11-15%
 - Moderate-High Risk: FRS 16-20%
 - High Risk: FRS >20%
 - Very High Risk: Acute Coronary Syndrome or known Coronary Artery Disease or significant multiple risk factors

This study will assess the rate at which CAC scoring reclassifies the FRS of a subject to a different risk category. To do so a descriptive table will be used to demonstrate the changes seen. The net reclassification improvement (NRI) will be calculated to describe further the amount of reclassification that is accomplished by using the CAC scoring method (19). Please see reference 19 for more information.

- Compare the Framingham Risk Score (FRS) to the Coronary Artery Calcium (CAC) score for enlisted subjects with at least 10 years of military service to determine how well the results correlate with one another.

- Linear Regression model will be used to determine if the FRS score correlates with the CAC score.
- Secondary Aims:

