 - A t-test will be used to compare CAC scores between each group in the following categories to see if there are associations between these categories and formation of calcified plaques:
 - Those meeting the criteria for metabolic syndrome vs. those not meeting criteria (See attachment 1 – Diagnostic Criteria for Metabolic Syndrome).
 - Those who lived in the dorms for >5 years compared to those living in the dorms for <5.
 - Those with PT test failures vs. those without.
 - Analysis of Variance (ANOVA) and/or Logistic regression will be used to compare CAC scores between each group in the following categories to see if there are associations between these categories and formation of calcified plaques:
 - Number of years of military service in the following groups: 10-14 years, 15-19 years 20-24 years and 25+ years
 - Those with 1 risk factor vs. 2 risk factors, vs. 3 risk factors, vs. 4 risk factors, vs. 5 risk factors (as listed in the inclusion criteria section).
 - The correlation between CAC and FRS scores will be described using multiple linear regression for the following categories:
 - Those meeting the criteria for metabolic syndrome vs. those not meeting criteria.
 - Those who lived in the dorms for >5 years compared to those living in the dorms for <5.
 - Those with PT test failures vs. those without.
 - Number of years of military service in the following groups: 10-14 years, 15-19 years 20-24 years and 25+ years.
 - Those with 1 risk factor vs. 2 risk factors, vs. 3 risk factors, vs. 4 risk factors, vs. 5 risk factors (as listed in the inclusion criteria section).

Source of Research Material per Participant:

Source of Research Material per Participant	Standard Care	Research Driven
Blood Sample – Hgb A1C	0	1 **
Blood Sample – Lipid Panel	0	1 **
Cardiac CT Scan	0	1
Outpatient Record Review	0	1
Subject Interview	0	1
Demographics	0	1

** In some subjects, the labs could be standard of care, but since the labs will not be standard of care for all subjects, they are listed here as research driven.

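### Most CAC scores will be zero, yet the plan compares them by t-test and linear regression, leaves its logistic option undefined, and names two different CAC variables for primary aim 3

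*Combined protocol and SAP*

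**What the plan says.** **Expected share with calcium.** The sample size paragraph of section 6.6 states: "for this study the estimated prevalence is 10" per cent. Section 6.1, on an Army screening cohort, reports: "The prevalence of coronary calcium was 20.6% for males and 4.3% for females".

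**Group comparisons (section 6.6, Secondary Aims).** For metabolic syndrome, dormitory years and PT failures: "A t-test will be used to compare CAC scores between each group in the following categories". The stated purpose is to look for associations with calcified plaque forming. The plan gives no variance form, transformation, rank method or two-part method. For years of service (four groups) and number of risk factors (five groups) it lists analysis of variance and/or logistic regression, without defining a binary outcome or saying how to choose.

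**FRS against CAC.** For primary aim 3, section 6.6 says: "Linear Regression model will be used to determine if the FRS score correlates with the CAC score". Section 6.2 words the same aim differently: "Compare FRS to the CAC percentage for age risk score". For secondary aim 2, section 6.2 speaks of cardiovascular risk by CAC, while section 6.6 says the correlation of the two scores will be described by multiple linear regression.

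**Women.** "Therefore an additional pilot sample of 30 female volunteers will be used to assess the prevalence detected in the female active duty population". Section 6.6 does not say whether they are pooled with the men in these analyses.

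**The concern.** A CAC score here is a spike at 0 plus a small number of positive values that can run from 1 to over 400. The mean of such a variable is set largely by the few highest scores. A t-test, an analysis of variance or a straight-line fit on the score therefore answers a question about mean score. The question the plan poses, whether plaque has formed, is mostly about who is above 0.

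Three things are at stake:

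- A real difference in the proportion with plaque may be missed, or a result may depend on one scan.
- Where logistic regression is allowed, the analyst can choose the method and the cut-point after seeing the data.
- Primary aim 3 can be reported on either of two variables, and nothing in the plan settles which.

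**Working it through.** **1. The plan's own figure.** n = 1.96² × p(1 − p) / 0.05². At p = 0.10: 3.8416 × 0.09 / 0.0025 = 138.3, the stated 138. At p = 0.085: 119.5, the stated 120. The 10% is therefore the working assumption. With 150 men and 10% dropout, 150 × 0.90 = 135 are analysed.

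**2. Share of zeros.**

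- Men at 10%: 135 × 0.90 = 121.5 zeros and 13.5 positive.
- Men at 20.6%: 135 × 0.794 = 107.2 zeros (79%) and 27.8 positive.
- Women, if pooled: 30 × 0.90 = 27, of whom 27 × 0.957 = 25.8 score 0. The pooled share of zeros is (121.5 + 25.8)/162 = 91%, or (107.2 + 25.8)/162 = 82% at the higher male prevalence.

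**3. Two-group comparisons.** The documents give no CAC distribution, group sizes or effect sizes, so everything in this step is assumed: positive scores lognormal with median 20 and log-SD 1.0, 1.5 or 2.0; 135 men split 68:67; two-sided 5% level. Power by simulation, with the three values in order of log-SD:

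| Assumed difference | t-test | CAC > 0 (Fisher) | Two-part test |
|---|---|---|---|
| 20% vs 5% positive, same burden | 46 / 29 / 16% | about 71% | 67–69% |
| 20% vs 5% positive, threefold median | 78 / 48 / 25% | 70–73% | 83 / 77 / 74% |
| 20% in both, fourfold median | 47 / 17 / 7% | about 4% | 83 / 46 / 28% |

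The two-part test adds the squared z for CAC > 0 to the squared rank-sum z among positives (2 degrees of freedom).

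The unstated form of the t-test also matters when groups are unequal. At 40:95, with the smaller group at 20% and the same burden, the pooled version has 52/41/32% and the unequal-variance version 24/10/5%, against 69% for CAC > 0.

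**4. FRS against CAC score.** Assumed: n = 135, lognormal FRS with median 5% and log-SD 0.6, 10% prevalence, and log-odds of CAC > 0 rising 0.8 per SD of log FRS.

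- Same burden: power about 46/34/28% for linear regression and about 70% for Spearman.
- Burden also rising with FRS (0.4 log units per SD): 73/55/43% and 72–75%.
- Type I error: 4.4–5.5% for both, so the linear test is sound in that respect.
- Deleting the single largest CAC score changes the linear verdict in about 20–30% of simulated trials, and Spearman's in about 10%. If each method instead loses its own most influential subject, the figures are 40–48% and 25–27%.

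**5. The variable in primary aim 3.** Section 6.2 names the percentage for age and section 6.6 the CAC score. Section 6.1 keeps them apart: "CAC scores are reported as a numerical value and a percentage for age that is then regarded in terms of risk categories". They need not relate to FRS in the same way, because a percentile for age takes age out while FRS puts it in: "The estimation takes gender, age, smoking status, systolic blood pressure, total cholesterol and HDL into account when predicting risk". No passage gives a percentile for a score of 0, which most men are expected to have.

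**The case against.** **The distribution is assumed.** This stands for every power figure. The share of zeros does follow from the plan's own prevalence, but it is an expectation. Section 6.7 requires at least one risk factor and sets no upper age limit, so fewer than 79% could score 0.

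**The t-test sometimes does as well or better.** This also stands. When burden rises with prevalence and skew is modest, it matches or beats CAC > 0 (78% against 70–73%). When only burden differs, CAC > 0 alone is almost blind. That argues for a supporting analysis of the scores. It does not rescue the t-test as the only method, since the two-part test does better in all three rows of the table.

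**Logistic regression is already in the plan.** It is listed for two of five comparisons, as an option, with no outcome defined.

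**Stronger readings that the documents do not support.** A reader might infer that the linear regression in primary aim 3 gives false positives; its type I error is close to nominal. A reader might infer that secondary aim 2 will produce spurious differences between categories; section 6.6 only describes that correlation and states no interaction term or test, so the risk arises only if such a test or interval is reported. A reader might take the largest-score deletion as the full measure of fragility; it favours Spearman, and the gap narrows when each method's own most influential subject is removed.

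**Conclusion.** The point holds, in conditional form. The planned methods suit the expected data poorly. For a pure difference in how many subjects have plaque, the t-test has roughly a quarter to two thirds of the power of a CAC > 0 comparison (16/71 = 0.23 to 46/71 = 0.65). For FRS against CAC with unchanged burden, linear regression has about 0.4 to 0.66 of Spearman's power (28/70 to 46/70). These ratios rest on assumed lognormal positive scores, assumed splits and assumed effects; they shrink or reverse when burden differs too.

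Two parts need no simulation: the logistic option has no outcome or selection rule, and primary aim 3 has two different variables. The looser wording of secondary aim 2 only needs aligning. Primary aim 1 (prevalence) and primary aim 2 (reclassification) do not use these tests and are unaffected. This should be fixed before analysis, but it does not threaten the study as a whole.

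**What to change.** 1. **Group comparisons (all five).** Make CAC > 0 against 0 the main analysis, by Fisher's exact test or its multi-group form, or by logistic regression with CAC > 0 as the stated outcome. Add one supporting rank or two-part analysis of the scores to capture burden. These replace the t-test and the open choice between analysis of variance and logistic regression.
2. **Primary aim 3.** Use Spearman correlation. Name one CAC variable, identically in sections 6.2 and 6.6. If it is the age percentile, state the value given to a score of 0.
3. **Secondary aim 2.** Keep it descriptive: Spearman correlations within each category, or regression with log(CAC + 1) as the stated outcome. Draw no inference about differences between categories from ordinary regression on raw CAC. Align the wording of 6.2 and 6.6.
4. **Women.** State either that these analyses are in men with the 30 women described separately, or that the women are pooled.

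The cost is wording only; no new data or subjects are needed. The downsides are that a raw mean difference in CAC is no longer the headline, and that CAC > 0 alone is insensitive to a burden-only difference, which is why the supporting analysis is needed.

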 - Coronary Artery Calcium Score Results
 - Framingham Risk Score
 - What the two scores mean
 - Lab Results
 - Lifestyle changes that can be made to decrease risk, i.e. smoking cessation, increasing exercise, dietary changes, etc.
- **For CAC >400:** The study coordinator or other research team member will place a referral into CHCS to the cardiology clinic for further evaluation. At this time a telephone-consult will be placed in the subject’s AHLTA record (See attachment 8 – Telephone Consult Template) and their PCM will be notified via an encrypted e-mail of their CAC results and their referral to cardiology (See attachment 9 – PCM Notification E-Mail Template). If subjects in this category are noted to have abnormal

HgbA1C and/or lipid panel their primary care manager (PCM) will be notified of abnormal results via encrypted e-mail. The HL&VC will contact the subject to schedule a follow-up appointment for the subject to be seen within 30 days, but no later than 60 days of the CAC scan. At the cardiology follow-up appointment, the following will be discussed:

- Coronary Artery Calcium Score Results
 - Framingham Risk Score
 - What the two scores mean
 - Lab Results
 - Lifestyle changes that can be made to decrease risk, i.e. smoking cessation, increasing exercise, dietary changes, etc.
 - Medications that could reduce risk of cardiac events in the future
 - Interventions, imaging or further testing that may be necessary to further evaluate/treat the subject
- **Measurements:**
 - Framingham Risk Score – (See attachment 10 – Framingham Risk Calculation Tables), includes age, systolic blood pressure, HDL level, Total Cholesterol level and smoking status
 - HgbA1C (if not previously tested within 3 months prior to study enrollment)
 - Lipid Panel (if not previously tested within 3 months prior to study enrollment)
 - Coronary Artery Calcium Score
 - Waist Circumference
 - Blood Pressure
 - **Demographic Info to be Collected:**
 - Branch of Military Service
 - Rank
 - Number of Years of Military Service
 - Number of Deployments >2 months
 - Number of Years living on base in Dormitories
 - Number of PT test failures
 - Number of Cardiac Risk Factors (Tobacco use, Diabetes, pre-diabetes, hypertension, waist circumference, hyperlipidemia)

6.5. Intervention/Treatment:

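### The comparison of CAC across years-of-service bands has no age term, so as planned it cannot separate a service gradient from ageing

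*Combined protocol and SAP*

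**What the plan says.** Section 6.6, Secondary Aims, plans: "Analysis of Variance (ANOVA) and/or Logistic regression will be used to compare CAC scores between each group". The first category listed is "Number of years of military service in the following groups: 10-14 years, 15-19 years 20-24 years and 25+ years". No covariate, age stratum or age-standardised outcome is named. Section 6.2 sets the aim, also without adjustment: "Compare CAC scores between each group in the following categories to see if there is associations between these categories and formation of calcified plaques".

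Age and age-referenced calcium do appear elsewhere in the protocol:

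- Section 6.4 (Measurements) says the Framingham Risk Score (FRS) "includes age, systolic blood pressure, HDL level, Total Cholesterol level and smoking status", so age will be in the data set.
- Section 6.1 says "CAC scores are reported as a numerical value and a percentage for age". That percentile feeds the risk categories in 6.6 and is named in primary aim 3, but not in this comparison.
- Section 6.6 also plans multiple linear regression by service band, to describe how CAC relates to FRS. That is a different question, and FRS does not isolate age.

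The sample size in 6.6 is set for the prevalence interval only. The plan does not say whether the 30 pilot women enter the service comparison.

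**The concern.** Each year served is also a year of age. If entry is at 18 or later (an assumption), a man with 25 years of service is at least 43, while the 10-14 band begins at the male age floor of 35 (section 6.7).

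The protocol's own reasoning makes calcium depend on age. It reports a percentile for age, and it justifies the sex-specific age floors by a lag of about ten years in female calcification. Section 6.1 also links older age to atherosclerosis at autopsy, although in a group the protocol regards as unrepresentative.

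What is at stake is the interpretation. Section 6.1 suggests that "the environment and lifestyle of the military may both select for and exacerbate cardiovascular risk". A rise in CAC across service bands would look like support for that idea even if service did nothing.

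**Working it through.** **1. The plan's own figures.** For a 95% interval of ±0.05, n = 1.96² × p(1−p)/0.05².

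- p = 0.085 gives 119.5, so 120, as stated.
- p = 0.10 gives 138.3, against 138 stated.
- 150 men less 10% leaves 135. At 10% prevalence that is 13.5, or about 14, men with CAC>0.

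There is no figure for the service comparison to reproduce.

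**2. Inputs.**

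- *From the documents:* 135 men; age floor 35; the four bands; prevalence 10% (section 6.6) or 20.6% (section 6.1: "The prevalence of coronary calcium was 20.6% for males and 4.3% for females", in Army personnel aged 39-45).
- *Assumed:* service uniform over 10-30 years, or declining (10 plus an exponential with mean 6, below 30); entry age 18 plus an exponential with mean 3 or 5 years; ages capped at 55; age odds ratio 1.05, 1.10 or 1.15 per year; positive scores lognormal (median 25, log-SD 1.6).
- *Model:* logit P(CAC>0) = logit(prevalence at age 42) + ln(OR) × (age − 42), with no service term. There were 3,000 simulated cohorts per setting, so the Monte Carlo standard error is at most √(0.25/3000) = 0.9 percentage points.

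**3. Size of the spurious contrast.** With mean entry delay 3, mean ages by band are 38.0, 39.0, 43.4 and 48.0 (uniform; age-service correlation 0.82) or 38.0, 38.8, 43.0 and 47.7 (declining; 0.70). The two lower bands are close in age because the floor of 35 admits only late entrants to the 10-14 band.

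A hand check for the uniform case is OR raised to the difference in mean age:

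| Contrast with 10-14 | Age gap (years) | Hand check at 1.05 / 1.10 / 1.15 | Simulated, all four service and entry settings |
|---|---|---|---|
| 25+ | 10.0 | 1.63 / 2.59 / 4.05 | 1.5-1.6 / 2.2-2.6 / 3.1-3.9 |
| 20-24 | 5.4 | 1.30 / 1.67 / 2.13 | 1.3 / 1.5-1.7 / 1.8-2.1 |
| 15-19 | 1.0 | 1.05 / 1.10 / 1.15 | 1.03-1.16 |

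With uniform service and 20.6% prevalence, CAC>0 in the 10-14 and 25+ bands is 18 v 26%, 15 v 32% and 14 v 38% for the three age odds ratios.

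**4. Rejection at 5% with no service effect.** Unadjusted logistic regression, three band indicators, per cent of studies at age OR 1.05 / 1.10 / 1.15:

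| Service, mean entry delay | Prevalence 20.6% | Prevalence 10% |
|---|---|---|
| Uniform, 3 | 11.6 / 30.6 / 57.6 | 8.6 / 18.1 / 37.1 |
| Uniform, 5 | 9.1 / 25.0 / 49.9 | 8.9 / 17.9 / 33.5 |
| Declining, 3 | 8.9 / 20.3 / 37.1 | 8.9 / 14.2 / 25.4 |
| Declining, 5 | 8.3 / 16.1 / 27.7 | 7.6 / 12.3 / 19.9 |

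- With no age effect, the unadjusted rate is 5.5-7.7%.
- With linear age added, it is 4.9-7.9% throughout.
- If the true age effect is non-linear (1.05 per year below 42, 1.15 above), the unadjusted rate is 17.5-38.3% and the linear-age model gives 5.5-7.5%.
- ANOVA on raw scores rejects in 3-8% (uniform) or 8-18% (declining). Adding linear age leaves 4-6% and 6-12%, so with declining service it does not reliably restore the nominal level.

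**5. Different assumptions.** A second simulation used 150 men, entry at about age 20 (SD 3, floor 17), uniform service, and ANOVA on the CAC>0 indicator. Crude odds ratios for 25+ against 10-14 were 1.7, 2.8 and 4.6. Rejection at 20.6% prevalence was 9, 26 and 53% unadjusted, against 4-5% with age.

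**6. Precision after adjustment.** For 25+ against 10-14, the standard error of the log odds ratio rises by 12-31%, to 0.84-1.51. Since exp(1.96 × 0.84) = 5.2 and exp(1.96 × 1.51) = 19.3, the 95% interval spans about 5- to 19-fold each way. For a true service odds ratio of 3 (ln 3 = 1.10), power for that contrast is about 11-26%.

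**The case against.** The strongest reply is that the aim asks only about associations, and the crude comparison answers that. The sentence on military environment is hedged background and is not tied to the service bands. The plan does not forbid a covariate; it is silent, and age is collected. All of this is right as far as it goes. The crude result is valid description, and the defect lies in the plan, not the data. But the plan followed as written gives only a service contrast that carries age with it, and the protocol's rationale makes a causal reading likely.

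The size is also open to challenge, and these points stand:

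- The prevalence labels refer to age 42. Under uniform service, overall prevalence in the simulated cohorts is 22-27% or 11-15%, so the 58% figure comes from a favourable setting.
- The second simulation gave odds ratios above the tabulated ranges, so those ranges are not bounds.
- At 1.05 per year the excess is small, and raw-score ANOVA with uniform service shows almost none.
- The adjusted analysis will rarely be informative. It removes a bias but does not supply power.

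Percentile for age could serve as the outcome instead, with no extra parameter. With about nine men in ten expected to score zero, it would add little to CAC>0, and the age correction would then rest on an external reference.

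**Conclusion.** The concern holds. Nothing in the protocol puts age into the service comparison. The direction of the bias needs only two things: age rises with service, and calcium rises with age.

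Its size depends on assumptions the documents cannot settle. Over the settings in steps 3 and 4, the spurious odds ratio for 25+ against 10-14 years runs from about 1.5 to 3.9, and false rejection by unadjusted logistic regression from about 8% to 58%. With age in the model the rate is 5-8%. The distortion lies mainly in the two upper bands.

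This is a secondary aim, and the prevalence estimate, reclassification and sample size are untouched. The change should be made, but it does not threaten the study's main result. No bias is claimed for dormitory years, PT failures, metabolic syndrome or number of risk factors.

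**What to change.** In section 6.6, for the years-of-service comparison only, write:

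> The main analysis will be logistic regression of CAC>0 on the four service bands with age in years as a continuous covariate, in men, fitted by penalised (Firth) likelihood because some bands may have few or no events. The 30 pilot women will be described separately. Unadjusted band results, including ANOVA, are descriptive. The result is exploratory.

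If women are pooled instead, say so and add sex. The essential change is the age term. The other details deal with sparse events and settle the open points on test and population. In 2,000 cohorts per setting (mean entry delay 3), the Firth likelihood-ratio test with age rejected in 2.8-5.0%.

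The cost is wording only: no new data, visits or participants. There are three drawbacks:

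- **Wide intervals**, as in step 6. Using continuous service instead of bands helps little (standard error over 15 years 0.97-1.47, against 1.00-1.51).
- **Few events.** At 10% prevalence with uniform service, the 10-14 band has no event in about 19-49% of studies. With declining service, the 25+ band expects only 1.2-2.5. The model should hold only age and service, plus sex if pooled.
- **Lost detail.** CAC>0 ignores the size of the score.
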